# 5. STATISTICAL ANALYSES

#### 5.1 Baseline data

Baseline data (i.e. patient demography and past history) will be described by treatment group for patients in the analysis population. **Table T3** will be used as a template for this.

Continuous variables will be summarised using the mean and standard deviation (SD) (or median and inter quartile range (IQR) if the distribution is skewed), and categorical data will be summarised as a number and percentage. The summary statistic headings given in **Table T3** are those we expect to use based on a-priori knowledge of the clinical measurements gained from previous studies. However, if distributional assumptions are not valid, changes will be made.

Any imbalances in the characteristics of the patients at the start of the study will be described but statistical tests for baseline imbalance will not be carried out.

#### 5.2 Additional descriptive data

Additional tables describing compliance, additional treatments, exposure to steroids, ocular examinations and results of tests performed throughout follow-up, by treatment group will be included (e.g. Tables T4-T15). The choice of summary statistics will be as for the baseline data. These data will only be described; no formal comparisons will be made.

#### 5.3 Primary and secondary outcome data

Primary and secondary outcome data will be described by treatment group for patients in the analysis population. The choice of summary statistics will be as for the baseline data. Treatment effects will be reported graphically with 95% confidence intervals (CIs), and with numerical details alongside (cf. Forest plot). **Figures F3 to F5** will be used as templates for this.

#### 5.3.1 Adjustment in models

The intention is to adjust all models for the stratification factors included in the randomisation: visual acuity level (low [54-67 ETDRS BCVA score] and high [68-85 ETDRS BCVA score]) as a fixed effect and centre as a random effect. If it is not possible to estimate a random effect for each centre due to small numbers of patients at some centres, these centres will be combined (e.g. centres with 1 or 2 patients will be grouped into one and centres with 3 or 4 patients will be grouped). If it is still not possible to estimate random effects for each of the (combined) centres, further groupings will be explored.

For continuous outcomes that are measured before the treatment has started at baseline as well as subsequently (e.g. BCVA); subsequent values will be modelled and the baseline value will be modelled as a covariate.

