# 3. STUDY POPULATION

The study population is all patients recruited into the trial satisfying the main eligibility criteria: aged between 18 and 60 years who have had visual impairment due to CSCR for at least four months (defined as subfoveal presence of SRF on OCT, characteristic appearance of CSCR on FFA and ICGA, and an investigator believes there is sufficient evidence that CSCR has been present for at least 4 months). For specific inclusion/exclusion criteria see **Figure F1**.

Recruitment over time against targets will be presented overall (Figure F2).

The planned sample size for the VICI study is 104 patients. This sample size is sufficient to detect a difference of 5 letters in BCVA between the eplerenone and placebo groups with 90% power and 5% significance (2-tailed), assuming that: the standard deviation is 9 letters; the correlation between baseline and any follow up assessment is 0.5; on average, there will be a minimum of 2 follow up assessments per patient with a correlation between BCVA on follow-up visits of 0.8; up to 15% dropout will occur over the 12 month period.

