- Time to event outcomes will be summarised by the median and IQR in each treatment group, estimated from Kaplan Meier curves. Outcomes will be compared using proportional hazards parametric survival models for interval-censored data. If the assumption of proportional hazards does not hold, other methods will be considered as appropriate. The choice of model used will depend on the outcome event and model assumptions. Treatment comparisons will be presented as hazard ratios (HRs) and 95% CI if a proportional hazards model is used, time ratios (TRs) and 95% CI if an accelerated failure time model is used, or odds ratios (OR) and 95% CI if a discrete time proportional odds model is used. Times will be censored using censoring variables defined below:

Outcome	Censor variable
Time to resolution of SRF	Date of last visit, if SRF did not resolve
Time to disease recurrence	Date of last visit, if SRF did not recur
Time to response (complete or partial)	Date of last visit, if disease did not resolve completely or partially
Time to incidence of CSCR in fellow eye	Date of last visit, if CSCR not present in fellow eye at any point by the end of follow-up

- Continuous longitudinal outcomes will be summarised as means and SDs (or medians and IQRs if distributions are skewed) at each time point. Outcomes will be compared using linear mixed effects methodology where the outcome of interest is collected at baseline, 4 weeks, 3, 6, 9 and 12 months, with the treatment group and study design variables fitted as per section 5.2.1, and patient terms fitted as random effects. Separate parameter estimates will be incorporated into models for 1) the mean baseline response across both treatment groups and 2) at each post-intervention time point for each treatment (i.e. saturated model with time fitted as a categorical variable). If the time x treatment interaction (postintervention) is not statistically significant at the 5% level an overall treatment effect will be reported. If the interaction is statistically significant the changes in treatment effect with time will be described. Different variance/covariance structures will be explored, and the structure that provides the best fit in terms of information criteria such as AIC, BIC and likelihood ratio tests will be used. Treatment comparisons will be presented as adjusted differences in means with 95% CI.

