#### Missing longitudinal data:

• For continuous data measured at multiple time points baseline values will be modelled jointly with those measured during follow-up, as described previously, thereby allowing all cases with at least one observation to be included. If the proportion of cases that do not have at least one observation is above 5% then multiple imputation methods will be considered (see above). If appropriate (the level of missingness is >20%) then any variables that are predictive of missingness will be identified, and if there is reason to suggest that an assumption of missing at random (MAR) given these variables is reasonable (especially likely if the variable was measured at baseline) then such variables will be adjusted for in the models of interest. These models can be shown to provide unbiased estimates of the treatment effect and moreover multiple imputation approaches would not be expected to recover any additional information.

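### The SAP leaves the role of baseline BCVA unresolved; if the joint model is fitted with a single VA-level effect, the primary standard error is about 4-12% too wide and power about 85-88% instead of 90%

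*SAP*

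**What the plan says.** Section 5.3.1 says that all models adjust for the stratification factors: "visual acuity level (low [54-67 ETDRS BCVA score] and high [68-85 ETDRS BCVA score]) as a fixed effect and centre as a random effect". Its next paragraph, which gives BCVA as the example, makes the follow-up values the response and the baseline value a covariate.

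Section 5.3.2, on continuous longitudinal outcomes, describes a different model: "Separate parameter estimates will be incorporated into models for 1) the mean baseline response across both treatment groups", together with separate parameters for each treatment at each follow-up visit. Section 5.3.8 agrees with it: "baseline values will be modelled jointly with those measured during follow-up", so that every case with at least one observation can be used. Section 5.3.2 brings in the design variables by pointing to a section 5.2.1, which does not exist; 5.3.1 appears to be meant. It leaves the covariance structure to be chosen by fit.

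No section mentions a VA-level-by-visit term, and none says that the VA-level effect is constant over visits.

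Section 3 gives the design inputs: "The planned sample size for the VICI study is 104 patients", enough to "detect a difference of 5 letters in BCVA between the eplerenone and placebo groups" with 90% power at a two-sided 5% level. It assumes that "the standard deviation is 9 letters" and that "the correlation between baseline and any follow up assessment is 0.5". It also assumes at least 2 follow-up assessments on average, correlated 0.8, and up to 15% dropout.

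**The concern.** VA level is a coarse version of BCVA at entry. When baseline BCVA is itself a response, the two strata are separated by construction at baseline by the full gap in the score. At follow-up the gap shrinks by regression to the mean, roughly in proportion to the baseline correlation. A single VA-level coefficient across all visits cannot fit both.

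The misfit passes into the estimated covariance matrix. It inflates the follow-up variance and weakens the estimated baseline-to-follow-up relation, which is what delivers the baseline adjustment in a joint model. Randomisation is stratified by VA level, so the treatment estimate is not biased. What is at stake is a reported standard error that is too large and a conservative primary test, in a trial whose sample size counts on the full gain from baseline.

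The text allows this model. A programmer who follows 5.3.2 and adds VA level as listed in 5.3.1 would fit one VA coefficient over baseline and follow-up.

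**Working it through.** **1. Reproduce the sample size.** Inputs from SAP section 3: SD 9, baseline correlation 0.5, follow-up correlation 0.8, r = 2 follow-ups, difference 5, dropout 15%.

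- Variance factor with full baseline adjustment: (1 + 0.8)/2 - 0.5² = 0.65.
- Variance of the adjusted follow-up mean: 81 × 0.65 = 52.65.
- Per arm: 2 × 10.51 × 52.65 / 25 = 44.3. Total 88.5; 88.5/0.85 = 104.
- Power at 44.2 per arm (104 × 0.85 / 2): SE = √(2 × 52.65/44.2) = 1.543; 5/1.543 - 1.96 = 1.28, so power is 0.900.

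The stated size reproduces. An analysis of follow-up values only, or of change scores, would need 146, so the 104 depends on full baseline adjustment.

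**2. One VA-level effect in the joint model.** The SAP does not give the baseline BCVA distribution. Assume here that it is normal with SD 9 and is cut at its mean, and that the stratum is set from the modelled baseline value.

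- Stratum gap at baseline: 2 × 9 × √(2/π) = 14.36 letters. At follow-up: 0.5 × 14.36 = 7.18.
- Within strata: baseline variance 81 - 14.36²/4 = 29.43; variance of the follow-up mean 0.9 × 81 - 7.18²/4 = 60.01; covariance 40.5 - 14.36 × 7.18/4 = 14.72.
- VA level by visit: conditional variance 60.01 - 14.72²/29.43 = 52.65, so the planned precision is kept.
- Single VA effect, maximum likelihood with unstructured covariance: the weights are 60.01 - 14.72 = 45.29 on the baseline gap and 29.43 - 14.72 = 14.71 on the follow-up gap. The forced effect is (45.29 × 14.36 + 14.71 × 7.18)/60.00 = 12.6 letters.
- Misfit: 14.36 - 12.60 = 1.76 at baseline and 7.18 - 12.60 = -5.42 at follow-up.
- Apparent moments: baseline variance 29.43 + 1.76²/4 = 30.2; follow-up variance 60.01 + 5.42²/4 = 67.35; covariance 14.72 - 1.76 × 5.42/4 = 12.33.
- Apparent conditional variance: 67.35 - 12.33²/30.2 = 62.3, against 52.65.
- Model SE: √(2 × 62.3/44.2) = 1.679, which is 1.088 times 1.543. The true sampling SD rises by only 0.2%.
- Power: (5 - 1.96 × 1.679)/(1.002 × 1.543) = 1.105, so 0.865.

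A simulation with 88 completers gives an SE ratio of 1.088 and power 0.870; with VA level by visit, power is 0.903.

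**3. Range over assumed baseline distributions** (unstructured covariance):

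| Assumed baseline BCVA | Gap at baseline / follow-up | SE ratio, r = 2 | Power, r = 2 | Power, r = 5 |
|---|---|---|---|---|
| Normal, cut at mean | 14.3 / 7.2 | 1.09 | 0.865 | 0.895 |
| Normal, mean 72 | 14.9 / 7.4 | 1.08 | 0.870 | 0.899 |
| Uniform 54-85 | 16.0 / 7.8 | 1.12 | 0.852 | 0.883 |
| Normal truncated to 54-85 (two variants) | 12.5-12.7 / 7.5-7.8 | 1.04-1.05 | 0.88 | 0.91 |

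The comparison is 0.900 for r = 2 and 0.925 for r = 5. The true sampling SD changes by at most 0.4% in every case.

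**4. Settings in which the loss shrinks or vanishes.**

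- Baseline as covariate: SE 1.552 with VA level and 1.544 without; power about 0.895 either way.
- Random intercept only: the single VA effect makes the SE about 3-5% wider than VA level by visit.
- Stratum set from a separate screening BCVA (normal case, r = 2): SE excess 4.9% at an assumed screening-to-baseline correlation of 0.9 and 2.5% at 0.8, against 8.8% when the modelled baseline value sets the stratum.

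**The case against.** The strongest reply is that the plan does not commit this error. In 5.3.1 the words about a fixed effect stand in contrast to the random effect for centre; they say nothing about time. A reader might infer that the SAP specifies a VA effect held constant over all visits, and hence that power falls to 85%. The documents do not support that: no section states such a constraint, and 5.3.1 itself describes a covariate model in which there is no loss. This stands, and the point is therefore conditional. It does not remove it, because 5.3.2 and 5.3.8 do describe the joint model, the handling of missing baseline values depends on it, and the list of separate parameters in 5.3.2 leaves VA level out.

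The size is also open to challenge. About 85% needs a near-uniform baseline; a normal distribution truncated to the 54-85 range gives 88%. The SAP does not say which measurement set the stratum, and section 3.2 allows up to a month between screening and randomisation. Section 3 calls 2 follow-ups a minimum and section 4.1 schedules 5, with which power stays near 90%. All of this stands and is reflected in the range. The covariance structure is open too, but a random intercept alone implies equal correlations and so cannot reproduce 0.5 and 0.8 together.

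Section 5.3.4 requires assumption checks and allows other methods if they fail. That is a possible route to repair, but it would mean changing the primary model after seeing data.

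A reader might also extend the loss to low luminance BCVA and CSRT. VA level is not a split of either measure, and no loss has been shown for them.

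**Conclusion.** The point holds in conditional form. The SAP contradicts itself on whether baseline BCVA is a covariate or a response, and it is silent on how VA level enters over time. If the joint model is fitted with a single VA-level effect, the treatment estimate is unbiased and the type I error is not inflated. The standard error is, however, about 4-12% too wide. Power is about 85-88% instead of 90% with 2 follow-ups, and about 88-91% instead of 92.5% with all 5.

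These figures assume the section 3 inputs, 88 completers, unstructured covariance, a stratum set from the modelled baseline BCVA, and one of the baseline distributions in the table.

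**What to change.** In 5.3.1, 5.3.2 and 5.3.8, state one role for baseline BCVA in the primary analysis, and correct the pointer to section 5.2.1.

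If baseline is a covariate, nothing further is needed on this point. If the joint model is kept for BCVA, add a sentence to 5.3.1 or 5.3.2 saying that VA level is fitted by visit, or at least with one effect at baseline and one common to follow-up.

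The cost is one sentence, one interaction term in the code and 1 to 5 more fixed-effect parameters, with no new data. In the calculations above it restores power to about 90%. Using the same term for low luminance BCVA and CSRT is optional.

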#### 5.3.2 Analysis models

All outcomes listed in the study protocol will be presented as per the template tables **Table T14** to **T18**. General methods of presentation and assessing treatment effects are outlined below. For all treatment comparisons, the placebo with usual care group will be the reference group. Details specific to each outcome are described as appropriate.

Each outcome will be considered under a certain data type, as outlined in the table below:

Date type	Outcomes
Binary	Proportion of patients with macular atrophy of the RPE Proportion of patients with reduced choroidal permeability
Continuous	Sub-retinal fluid thickness Area of macular RPE hypoautofluorescence Patient-reported visual function (VFQ-25) Choroidal thickness
Time to event	Time to resolution of SRF Time to disease recurrence Time to complete or partial resolution Incidence of CSCR in fellow eye
Longitudinal	BCVA (primary) Low luminance BCVA CSRT
Descriptive	Systemic and ocular adverse events Classification of all study eyes as complete, partial or no resolution of SRF Classification of all study eyes by each FFA phenotype

Each type of data will be summarised and compared between the groups according to the following:

- **Binary outcomes** will be presented as numbers and percentages of patients in each treatment group experiencing the outcome at 12 months. Outcomes will be compared between treatment groups using logistic regression, with treatment comparison estimates presented as adjusted odds ratios (OR) and 95% confidence intervals (95% CI). Formal statistical comparisons of treatment effects will only be performed if more than ten patients in total experience the outcome (with at least one event in each treatment group).
- Continuous outcomes measured 12 months only (with or without baseline values) will be summarised by the mean change and SD in each treatment group if distributions are approximately normal, or the median and IQR if data are non-normal. In patient-reported visual function, mean and SD at 12 months will be summarised and models adjusted for baseline. Outcomes will be compared using linear regression. For untransformed data treatment comparisons will be presented as adjusted differences in means with 95% CI, and for logarithmically transformed data as adjusted geometric mean ratios (GMRs) with 95% CI.
- Time to event outcomes will be summarised by the median and IQR in each treatment group, estimated from Kaplan Meier curves. Outcomes will be compared using proportional hazards parametric survival models for interval-censored data. If the assumption of proportional hazards does not hold, other methods will be considered as appropriate. The choice of model used will depend on the outcome event and model assumptions. Treatment comparisons will be presented as hazard ratios (HRs) and 95% CI if a proportional hazards model is used, time ratios (TRs) and 95% CI if an accelerated failure time model is used, or odds ratios (OR) and 95% CI if a discrete time proportional odds model is used. Times will be censored using censoring variables defined below:

Outcome	Censor variable
Time to resolution of SRF	Date of last visit, if SRF did not resolve
Time to disease recurrence	Date of last visit, if SRF did not recur
Time to response (complete or partial)	Date of last visit, if disease did not resolve completely or partially
Time to incidence of CSCR in fellow eye	Date of last visit, if CSCR not present in fellow eye at any point by the end of follow-up

- Continuous longitudinal outcomes will be summarised as means and SDs (or medians and IQRs if distributions are skewed) at each time point. Outcomes will be compared using linear mixed effects methodology where the outcome of interest is collected at baseline, 4 weeks, 3, 6, 9 and 12 months, with the treatment group and study design variables fitted as per section 5.2.1, and patient terms fitted as random effects. Separate parameter estimates will be incorporated into models for 1) the mean baseline response across both treatment groups and 2) at each post-intervention time point for each treatment (i.e. saturated model with time fitted as a categorical variable). If the time x treatment interaction (postintervention) is not statistically significant at the 5% level an overall treatment effect will be reported. If the interaction is statistically significant the changes in treatment effect with time will be described. Different variance/covariance structures will be explored, and the structure that provides the best fit in terms of information criteria such as AIC, BIC and likelihood ratio tests will be used. Treatment comparisons will be presented as adjusted differences in means with 95% CI.
- **Descriptive outcomes** will be described using the mean and SD, the median and IQR (if data are non-normal) or numbers and percentages, by group and overall.

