#### 5.3.3 Statistical significance

For hypothesis tests two-tailed p-values<0.05 are considered statistically significant. Likelihood ratio tests will be used in preference to Wald tests for hypothesis testing.

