#### 5.3.9 Multiple testing

No formal adjustment will be made for multiple testing. However as previously described formal statistical comparisons will not be made for outcomes with low event rates and only pre-specified subgroup analyses will be performed. Consideration will be taken in interpretation of results to reflect the number of statistical tests performed and the consistency, magnitude and direction of treatment estimates for different outcomes.

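### Binary secondary outcomes: the condition of at least one event per arm leaves untested the most extreme split for any event total above ten

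*SAP*

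**What the plan says.** SAP section 5.3.2 lists two outcomes as binary: "Proportion of patients with macular atrophy of the RPE Proportion of patients with reduced choroidal permeability". Both are assessed at 12 months and shown as numbers and percentages by group. For the comparison, "Outcomes will be compared between treatment groups using logistic regression", giving an adjusted odds ratio with a 95% CI. Section 5.3.1 intends adjustment for visual acuity level as a fixed effect and centre as a random effect.

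A formal comparison is allowed only if "more than ten patients in total experience the outcome (with at least one event in each treatment group"). Section 5.3.9 refers back to this rule and gives its purpose: "formal statistical comparisons will not be made for outcomes with low event rates". Section 5.3.3 sets the level ("two-tailed p-values<0.05 are considered statistically significant") and the type of test: "Likelihood ratio tests will be used in preference to Wald tests for hypothesis testing". No method is named for an arm in which nobody, or everybody, has the outcome.

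**The concern.** The two conditions differ in kind. Whether more than ten patients have the outcome depends on the pooled count and does not look at which arm did better. Whether each arm has an event depends on how the events divide between the arms, which is the result being tested. Once the total exceeds ten, the second condition can stop a comparison only when every event is in the same arm.

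An empty arm does make the maximum-likelihood odds ratio and its Wald interval inestimable, and that is presumably the motive. It is a limit of one estimator and does not mean that the data say little. The stated purpose, low event rates, is already served by the total: 20 v 0 is not a low event rate.

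The rule also looks only at events. If every patient in one arm has the outcome, both conditions can be met, yet the odds ratio is just as inestimable.

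At stake is whether a clear benefit or harm on either of these two outcomes could end without an estimate, interval or p-value. A method chosen after the empty arm had been seen would be post hoc.

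**Working it through.** **Arm size.** "The planned sample size for the VICI study is 104 patients" (SAP section 3), allocated 1:1. The stated inputs are a 5-letter difference, SD 9, baseline correlation 0.5, two follow-ups correlated 0.8, 90% power and two-sided 5%.

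- Variance factor: (1 + 0.8)/2 − 0.5² = 0.65, so the SD is 9 × √0.65 = 7.26.
- This needs 45 per arm, 90 in total. 90 × 1.15 = 103.5, which rounds up to the stated 104. (Dividing by 0.85 gives 106. The gap of two has no bearing here.)
- With 15% dropout, 104 × 0.85 = 88.4, so about 44 per arm at 12 months.

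**What is tested and what is not.** Two-sided Fisher p-values at 44 per arm, as a stand-in for the adjusted logistic model:

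| Total events | All in one arm (barred) | One event in the other arm (tested) |
|---|---|---|
| 11 | 11 v 0: p = 0.0005 | 10 v 1: p = 0.007 |
| 15 | 15 v 0: p = 0.00001 | 14 v 1: p = 0.0003 |
| 20 | 20 v 0: p = 0.0000001 | 19 v 1: p = 0.000004 |

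For the first row, Fisher p = 2 × C(44,11)/C(88,11) = 0.00048. At 52 per arm it is 0.00054.

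The likelihood ratio test that section 5.3.3 prefers can still be computed with an empty arm. For 11 v 0 the unadjusted version gives p = 0.00004. Taking the odds ratio as empty arm against the other, its 95% profile-likelihood upper limit is 0.15.

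**How often the per-arm condition acts alone.** With rates p1 and p2, the probability is (1 − p2)^44 × P(X1 > 10) plus the mirror term, where X1 is binomial(44, p1). The mirror term is negligible in the rows below. Because 11 v 0 is already significant, every table barred by this condition alone is significant, so this probability equals the power lost.

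The rates are assumptions. Power is by exact enumeration, with Fisher p < 0.05:

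| Assumed rates | (1 − p2)^44 × P(X1 > 10) | Power, more-than-ten condition only | Power, full rule | Loss (points) |
|---|---|---|---|---|
| 25% v 10% | 0.0097 × 0.558 | 33.8% | 33.3% | 0.5 |
| 20% v 4% | 0.166 × 0.254 | 35.0% | 30.8% | 4.2 |
| 25% v 5% | 0.105 × 0.558 | 60.2% | 54.4% | 5.8 |
| 25% v 2% | 0.411 × 0.558 | 64.4% | 41.5% | 22.9 |
| 30% v 1% | 0.643 × 0.811 | 84.2% | 32.1% | 52.2 |

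At equal rates of 25% the condition almost never acts (probability below 0.001%), and power is 2.6% with or without it. At those rates it gives no useful protection against false positives.

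**Whether another section rescues the rule.** Section 5.3.4 says other methods will be sought if model assumptions fail, but section 5.3.2 has already barred the comparison, so no model is fitted whose assumptions could fail. Section 5.3.9 speaks only of low event rates.

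**The case against.** The strongest case for leaving the rule alone has five parts.

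- **It is a pre-specified, symmetric safeguard.** Logistic regression cannot give a finite odds ratio with an empty arm, and falling back on description cannot produce a false positive. This is true, but a named alternative method would protect the model equally well.
- **The trigger is improbable.** The loss is large only when one arm's rate is about 2% or lower and the other's 25% or higher, and nothing in the SAP points to such rates. Section 4.2 (items 5 and 8) takes both outcomes from the 12-month assessment without excluding eyes already positive at baseline, which makes an empty arm less likely. This stands, and it limits the weight of the point.
- **The more-than-ten threshold can cost more.** At 20% v 4% it lowers power from 54.7% to 35.0%, and at 25% v 5% from 69.5% to 60.2%. This is also true, but that threshold is blind to the direction of the result and matches the reason the SAP gives.
- **Little is hidden.** Counts and percentages appear whatever the rule decides, so a reader would see 0 v 11.
- **The all-events arm is remote.** At a true rate of 90%, all 44 patients have the outcome with probability 0.9^44, about 1%. Section 5.3.4 offers a general, unspecific way out there.

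A reader might infer that the test is withheld whenever the treatment difference is largest. The SAP does not support that. The statement holds only for a fixed event total: 1 v 40 is a far larger difference than 0 v 11 and would be tested.

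**Conclusion.** The point holds in a narrow form. Among all splits of a given total above ten, the rule bars the most extreme one and tests the weaker ones, and no other section supplies a method for it. The p-values rest on 44 analysed per arm and on Fisher's test in place of the adjusted model.

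The power losses rest on assumed event rates. They run from 0.5 to 6 points unless one arm's rate is about 2% or lower, and reach 23 to 52 points in the two most extreme scenarios shown.

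A reader might take those last figures as the expected loss in this trial. With no event rates in the SAP, they show only what the rule can do. Two secondary outcomes are affected. The primary outcome and the sample size are not.

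**What to change.** In SAP section 5.3.2, keep the more-than-ten threshold as defined, delete the bracketed per-arm condition, and add:

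*If either arm has no events, or no non-events, the comparison will use Firth penalised (or exact) logistic regression adjusted for visual acuity stratum, with a profile-likelihood (or exact) 95% CI, on observed data.*

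One of the two methods should be chosen when the text is written. The cost is one sentence and a standard procedure. In the empty-cell case a penalised odds ratio is shrunk and its interval wide, and the centre random effect may have to be dropped. Multiple imputation, which section 5.3.8 would consider above 5% missing, may also have to be dropped, which is why the sentence specifies observed data.

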#### 2.3 Primary outcome

The primary outcome is BCVA over a 12 month period.

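### A 5% treatment-by-time test decides whether an overall BCVA effect is promised, and the SAP does not say what answers the primary question when that test is significant

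*SAP*

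**What the plan says.** Section 2.3 defines the outcome without naming a visit: "The primary outcome is BCVA over a 12 month period". Section 4.1 lists five post-randomisation BCVA assessments, at 4 weeks and at 3, 6, 9 and 12 months. Section 3 sizes the trial for one between-group difference: "This sample size is sufficient to detect a difference of 5 letters in BCVA between the eplerenone and placebo groups with 90% power", at a two-sided 5% level.

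Section 5.3.2 fits a mixed model with a separate treatment effect at each follow-up visit and then branches on the treatment-by-time interaction. If the interaction "is not statistically significant at the 5% level an overall treatment effect will be reported", the reader gets one summary. In the other case: "If the interaction is statistically significant the changes in treatment effect with time will be described". That branch names no overall estimate, key visit or decision rule.

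Three other places bear on the point:

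- Section 5.3.3 treats two-tailed p-values below 0.05 as significant, and section 5.3.9 makes no multiplicity adjustment.
- The shells for Table T16 (BCVA) and Table T18 (low luminance BCVA and CSRT) have rows for each visit, for the interaction test and for an overall estimate. No footnote makes the overall row conditional.
- Section 1.4 calls the shells a guide, but also expects the content of the final tables to agree with them.

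**The concern.** The trial asks one superiority question and is powered for one contrast. Under the branching rule, the data decide whether that contrast is the primary result. If the interaction is significant, the SAP leaves up to five visit-specific estimates and p-values, with nothing said in advance about which of them carries the conclusion.

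The branch is most likely to be taken when the drug works but its effect builds up over the year. Visits run from 4 weeks to 12 months, so this pattern is plausible, although the SAP states no expected time course. A trial that meets its own 5-letter target on average could then report without a designated primary test. If there is no effect, the same branch leaves room to read any one significant visit as a positive result.

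**Working it through.** **Inputs from the SAP.** Section 3 gives 104 patients, a difference of 5 letters, 90% power, two-sided 5%, "the standard deviation is 9 letters", "the correlation between baseline and any follow up assessment is 0.5", a minimum average of 2 follow-up assessments with correlation 0.8 between them, and up to 15% dropout. Section 3.2 gives 1:1 allocation. Section 4.1 gives five follow-up visits.

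**Step 1: reproduce the sample size.** For a baseline-adjusted mean of r follow-ups,

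n per arm = 2 (1.960 + 1.282)² × SD² × f / δ², with f = [1 + (r − 1)ρ]/r − ρ_b².

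With r = 2, ρ = 0.8 and ρ_b = 0.5: f = 0.90 − 0.25 = 0.65, and n = 2 × 10.507 × 81 × 0.65 / 25 = 44.26. Then 2 × 44.26 / 0.85 = 104.1, which matches 104.

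The alternatives tried do not match:

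| Target | f | Total N |
|---|---|---|
| Mean of two follow-ups, baseline-adjusted | 0.65 | 104 |
| Single visit, baseline-adjusted | 0.75 | 120 |
| Mean of five follow-ups, baseline-adjusted | 0.59 | 95 |
| Mean of two, unadjusted or change score | 0.90 | 144 |

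The powered quantity is therefore an average over follow-up, not a single visit.

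**Step 2: power of the average when it is always tested.** After dropout there are 104 × 0.85 / 2 = 44.2 per arm. With all five visits, f = 0.59 and SE = 9 × √(2 × 0.59 / 44.2) = 1.47. Then 5 / 1.47 − 1.96 = 1.44, which is 92.5% power. With two follow-ups it is 90%. A time trend with the same 5-letter mean does not change this.

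**Step 3: how often the interaction is significant.** Assume equal correlation ρ between all follow-up visits and full attendance. The test has 4 degrees of freedom (critical value 9.49) and non-centrality

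λ = (n/2) × Σ(δ_t − mean δ)² / [SD²(1 − ρ)].

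At ρ = 0.8 the denominator is 81 × 0.2 = 16.2.

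- Effects of 4, 4.5, 5, 5.5, 6 letters: sum of squares 2.5, λ = 22.1 × 2.5 / 16.2 = 3.41.
- Effects of 3, 4, 5, 6, 7 letters: sum of squares 10, λ = 22.1 × 10 / 16.2 = 13.64.

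| Pattern (mean 5 letters) | ρ = 0.6 | 0.7 | 0.8 | 0.9 |
|---|---|---|---|---|
| Flat | 5% | 5% | 5% | 5% |
| 4 to 6 letters | 15% | 19% | 28% | 53% |
| 3 to 7 letters | 53% | 67% | 86% | 99% |

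**Step 4: missed visits.** If each patient contributes a random two of the five visits, the 3-to-7 pattern keeps about a quarter of its within-patient information. The ten visit pairs have squared differences summing to 5 × 10 = 50, so the average pair gives 5, and half of that is 2.5 in place of 10. Hence λ is about 3.41 and the probability about 28%. Other ways of computing it give 26% to 30%. With three of five visits it is about 54%.

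**Step 5: chance that the average is significant and the SAP also promises to report it.** In 4,000 simulated trials per pattern (44 per arm, ρ = 0.8, full attendance), this was 87% for a flat effect, 66% for 4 to 6 letters and 13% for 3 to 7 letters.

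**Step 6: type I error.** With no true effect, the non-significant branch contributes about 0.95 × 5% = 4.75%. In the significant branch about 35% of trials show at least one visit with p < 0.05, adding 0.05 × 35% = 1.75%. The total is about 6.5%, against 5.0% for the average alone. If only the 12-month visit is read in that branch, the total is about 5.2%.

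**The case against.** A reader might infer that the overall effect is withheld when the interaction is significant, or that the primary result vanishes. The SAP does not support either. Section 5.3.2 says when an overall effect will be reported; it never says that it will otherwise be suppressed. The T16 and T18 shells carry an overall row with no condition attached, and section 1.4 expects final tables to agree with the shells. An overall figure may well appear. This part of the objection stands, but it does not close the gap: the shell fits either branch, and nothing says that the overall row is primary when the interaction is significant.

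Nor would a real benefit go unseen. In the 3-to-7 case, among trials with a significant interaction, about 99% are significant at 12 months and on average 3.9 of the five visits are significant. The loss is one of pre-specification, not of detection.

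The probabilities also depend on growth patterns that the SAP does not state, on equal correlation between visits (section 5.3.2 leaves the structure to be chosen by fit) and on attendance. The ranges above are therefore wide. The type I inflation is small and needs a reading that the SAP does not itself adopt; section 5.3.9 promises cautious interpretation.

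Finally, equal weighting over five unequally spaced visits is a choice that the SAP has not made. Other weightings also fit an outcome defined over 12 months.

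**Conclusion.** The point holds as a gap in the primary analysis rule and should be fixed. A preliminary 5% test decides whether the contrast behind the 104 patients is promised as the result, and the other branch has no designated estimate or test.

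That branch is taken in 5% of trials even when the effect is constant. For a 5-letter mean benefit with full attendance and correlation 0.8, it is taken in about 28% for a rise from 4 to 6 letters and about 86% for a rise from 3 to 7. The figures move substantially with correlation and fall when visits are missed. The defect in the rule does not depend on any one pattern; only its likely cost does. The rise in type I error, to about 6.5% at most on the reading examined, is secondary.

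**What to change.** Replace the two branching sentences in section 5.3.2 with a statement along these lines: the primary result is the treatment difference averaged over the post-randomisation visits, with weights fixed in advance (for example, equal over the five visits), estimated from the saturated model and reported with its 95% CI and p-value whatever the interaction test shows. The interaction test and the visit-specific differences are supportive.

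State that the overall row of Table T16 is always completed, and apply the same rule to low luminance BCVA and CSRT in Table T18.

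The cost is an amendment to the SAP text, documented and re-approved as section 1.2 requires. The sample size stays at 104, with about 90% power on the SAP's own inputs and 92.5% if all five visits contribute. The downside is that an average can mask a time trend, but the visit rows of Table T16 and Figure F4 would still show it.
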